#### 5.2.6.1.4 Adverse events of special interest

The term adverse events of special interest (AESI) relates to any specific AE that has been identified at the project level as being of particular concern for prospective safety monitoring and safety assessment within this trial, e.g. the potential for AEs based on knowledge from other compounds in the same class. AESIs need to be reported to the sponsor's Pharmacovigilance Department within the same timeframe that applies to SAEs, please see Section [5.2.6.2.2](#).

Hepatic injury is considered an AESI in this trial. A hepatic injury is defined by the following alterations of hepatic laboratory parameters:

- An elevation of AST (aspartate transaminase) and/or ALT (alanine transaminase)  $\geq 3$ -fold ULN combined with an elevation of total bilirubin  $\geq 2$ -fold ULN measured in the same blood sample, or
- Aminotransferase (ALT, and/or AST) elevations  $\geq 10$  fold ULN

These lab findings constitute a hepatic injury alert and the subjects showing these lab abnormalities need to be followed up according to the 'DILI checklist' provided in the ISF. In case of clinical symptoms of hepatic injury (icterus, unexplained encephalopathy, unexplained coagulopathy, right upper quadrant abdominal pain, etc.) without lab results (ALT, AST, total bilirubin) available, the Investigator should make sure that these parameters are analysed, if necessary in an unscheduled blood test. Should the results meet the criteria of hepatic injury alert, the procedures described in the DILI checklist should be followed.

#### 5.2.6.1.5 Intensity (severity) of AEs

The intensity (severity) of the AE should be judged based on the following:

Mild: Awareness of sign(s) or symptom(s) that is/are easily tolerated  
Moderate: Sufficient discomfort to cause interference with usual activity  
Severe: Incapacitating or causing inability to work or to perform usual activities

#### 5.2.6.1.6 Causal relationship of AEs

Medical judgment should be used to determine the relationship, considering all relevant factors, including pattern of reaction, temporal relationship, de-challenge or re-challenge, confounding factors such as concomitant medication, concomitant diseases and relevant history.

Arguments that may suggest that there is a reasonable possibility of a causal relationship could be:

- The event is consistent with the known pharmacology of the drug
- The event is known to be caused by or attributed to the drug class
- A plausible time to onset of the event relative to the time of drug exposure
- Evidence that the event is reproducible when the drug is re-introduced

Proprietary confidential information © 2021 Boehringer Ingelheim International GmbH or one or more of its affiliated companies

- No medically sound alternative aetiologies that could explain the event (e.g. pre-existing or concomitant diseases, or co-medications)
- The event is typically drug-related and infrequent in the general population not exposed to drugs (e.g. Stevens-Johnson syndrome)
- An indication of dose-response (i.e. greater effect size if the dose is increased, smaller effect size if dose is reduced)

Arguments that may suggest that there is no reasonable possibility of a causal relationship could be:

- No plausible time to onset of the event relative to the time of drug exposure is evident (e.g. pre-treatment cases, diagnosis of cancer or chronic disease within days / weeks of drug administration; an allergic reaction weeks after discontinuation of the drug concerned)
- Continuation of the event despite the withdrawal of the medication, taking into account the pharmacological properties of the compound (e.g. after 5 half-lives). Of note, this criterion may not be applicable to events whose time course is prolonged despite removing the original trigger
- Additional arguments amongst those stated before, like alternative explanation (e.g. situations where other drugs or underlying diseases appear to provide a more likely explanation for the observed event than the drug concerned)
- Disappearance of the event even though the trial drug treatment continues or remains unchanged

## 5.2.6.2 Adverse event collection and reporting

### 5.2.6.2.1 AE collection

Upon enrolment into a trial, the subject's baseline condition is assessed (for instance, by documentation of medical history/concomitant diagnoses), and relevant changes from baseline are subsequently noted.

Subjects will be required to report spontaneously any AEs as well as the time of onset, end time, and intensity of these events. In addition, each subject will be regularly assessed by the medical staff throughout the clinical trial and whenever the investigator deems necessary. As a minimum, subjects will be questioned for AEs (and concomitant therapies) at the time points indicated in the [Flow Chart](#). Assessment will be made using non-specific questions such as 'How do you feel?'. Specific questions will be asked wherever necessary in order to more precisely describe an AE.

A carefully written record of all AEs shall be kept by the investigator in charge of the trial. Records of AEs shall include data on the time of onset, end time, intensity of the event, and any treatment or action required for the event and its outcome.

Proprietary confidential information © 2021 Boehringer Ingelheim International GmbH or one or more of its affiliated companies

The following must be collected and documented on the appropriate CRF(s) by the investigator:

- From signing the informed consent onwards until an individual subject's end of trial:
  - All AEs (serious and non-serious) and all AESIs
  - The only exception to this rule are AEs (serious and non-serious) and AESIs in Phase I trials in healthy volunteers, when subjects discontinue from the trial due to screening failures prior to administration of any trial medication. In these cases, the subjects' data must be collected at trial site but will not be entered in the CRF or trial database and will not be reported in the CTR.
- After the individual subject's end of trial:
  - The investigator does not need to actively monitor the subject for new AEs but should only report any occurrence of cancer and related SAEs and related AESIs of which the investigator may become aware of by any means of communication, e.g. phone call. Those AEs should, however, not be reported in the CRF

#### **5.2.6.2.2 AE reporting to the sponsor and timelines**

The Investigator must report SAEs, AESIs, and non-serious AEs which are relevant for the reported SAE or AESI, on the BI SAE form via fax immediately (within 24 hours) to the sponsor's unique entry point (country specific contact details will be provided in the ISF). The same timeline applies if follow-up information becomes available. In specific occasions the Investigator could inform the sponsor upfront via telephone. This does not replace the requirement to complete and fax the BI SAE form.

With receipt of any further information to these events, a follow-up SAE form has to be provided. For follow-up information, the same rules and timeline apply as for initial information.

#### **5.2.6.2.3 Information required**

All (S)AEs, including those persisting after the individual subject's end of trial, must be followed up until they have resolved, have been assessed as 'chronic' or 'stable', or no further information can be obtained.

#### **5.2.6.2.4 Pregnancy**

Once the male subject has been enrolled in the clinical trial and has taken trial medication, and if a partner of the male trial participant becomes pregnant, the investigator must report any drug exposure during pregnancy in a partner of the male trial participant immediately (within 24 hours) by means of Part A of the Pregnancy Monitoring Form to the sponsor's unique entry point, after a written consent of the pregnant partner.

The outcome of the pregnancy associated with the drug exposure during pregnancy must be followed up and reported to the sponsor's unique entry point on the Pregnancy Monitoring Form for Clinical Trials (Part B). The ISF will contain the Pregnancy Monitoring Form for

Proprietary confidential information © 2021 Boehringer Ingelheim International GmbH or one or more of its affiliated companies

Clinical Trials (Part A and Part B) as well as non-trial specific information and consent for the pregnant partner.

As pregnancy itself is not to be reported as an AE, in the absence of an accompanying SAE and/or AESI, only the Pregnancy Monitoring Form for Clinical Trials and not the SAE form is to be completed. If there is an SAE and/or AESI associated with the pregnancy, an SAE form must be completed in addition.

## **5.3 DRUG CONCENTRATION MEASUREMENTS AND PHARMACOKINETICS**

### **5.3.1 Assessment of pharmacokinetics**

Date and clock times of drug administration and pharmacokinetic sampling will be recorded in the eCRFs.

Exact times of blood sampling will be derived from the electronic data capturing system ClinSpark and documented in the eCRFs by the medical personnel or sent as electronic files to the trial data manager. The actual sampling times will be used for determination of pharmacokinetic parameters.

PK sampling times and periods may be adapted during the trial based on information obtained during trial conduct (e.g. as a result of preliminary PK data), including addition of samples and visits, as long as the total blood volume taken per subject does not exceed 500 mL. Such changes would be implemented via non-substantial CTP Amendments.

### **5.3.2 Methods of sample collection**

#### **5.3.2.1 Blood sampling for pharmacokinetic analysis**

For quantification of BI 765080 concentrations in serum, approximately 3.0 mL of blood will be drawn from an antecubital or forearm vein into a serum collection tube (SST II Advance tube or equivalent) at the times indicated in the [Flow Chart](#). Blood will be withdrawn by means of either an indwelling venous catheter or by venepuncture with a metal needle.

[figure not shown]
The sample tubes will be inverted six times without shaking and left upright for at least 30 minutes to allow the sample to thoroughly clot. Serum is prepared by centrifugation for approximately 10 -15 minutes at approximately 1500 g to 2000 g at room temperature. Immediately transfer 0.5 mL serum from the collection tube into each of the labelled cryotubes.

[figure not shown]
At a minimum, the sample tube labels should list BI trial number, subject number, visit, and planned sampling time, aliquot #1 or #2, serum, and PK.

The time each aliquot was placed in the freezer will be documented. Until transfer on dry ice to the analytical laboratory, the aliquots will be stored upright at approximately -70°C/-94°F or below at the trial site. The second aliquot will be transferred to the analytical laboratory after the bioanalyst has acknowledged safe arrival of the first aliquot. At the analytical laboratory, the serum samples will be stored at approximately -70°C/-94°F or below until analysis.

Proprietary confidential information © 2021 Boehringer Ingelheim International GmbH or one or more of its affiliated companies

After completion of the trial, the serum samples may be used for further methodological investigations (e.g., for stability testing). However, only data related to the analyte will be generated by these additional investigations. The study samples will be discarded after completion of the additional investigations, but not later than 5 years after the CTR is archived.

## **5.5            BIOBANKING**

Not applicable.

## **5.6 OTHER ASSESSMENTS**

Not applicable.

## **5.7 APPROPRIATENESS OF MEASUREMENTS**

All measurements performed during this trial are standard measurements and will be performed in order to monitor subjects' safety and to determine pharmacokinetic [REDACTED] [REDACTED] parameters in an appropriate way. The scheduled measurements will allow monitoring of changes in vital signs, standard laboratory values, and ECG parameters that might occur as a result of administration of trial medication. The safety assessments are standard, are accepted for evaluation of safety and tolerability of an orally administered drug, and are widely used in clinical trials. The pharmacokinetic parameters and measurements outlined in Section 5.4 are generally used assessments of drug exposure. [REDACTED]  
[REDACTED]

## **6. INVESTIGATIONAL PLAN**

### **6.1 VISIT SCHEDULE**

Exact times of measurements outside the permitted time windows will be documented. The acceptable time windows for screening and the end of trial examination are provided in the [Flow Chart](#).

Study measurements and assessments scheduled to occur ‘before’ trial medication administration on Day 1 are to be performed and completed within a 3 h-period prior to the trial drug administration (including blank values for PK and biomarkers).

The acceptable deviation from the scheduled time for vital signs and ECG will be:

- $\pm 20$  min up to and including 12 h
- $\pm 30$  min from 12h up to and including 48 h
- $\pm 60$  min from 48 h up to Day 8
- $\pm 4$ h from Day 8 onwards up to the last measurements

The tolerance for blood sampling for PK, [REDACTED] and laboratory parameters will be:

- $\pm 1$  min up to and including 30 min
- $\pm 5$  min from 30 min up to and including 12 h
- $\pm 15$  min from 12 h up to and including 48 h
- $\pm 60$  min from 48 h up to Day 8
- $\pm 4$ h from Day 8 onwards up to the last measurements

If several activities are scheduled at the same time point in the [Flow Chart](#), ECG should be the first and meal the last activity. Furthermore, if several measurements including venipuncture are scheduled for the same time, venipuncture should be the last of the measurements due to its inconvenience to the subject and possible influence on physiological parameters.

For planned individual blood concentration sampling times, refer to the [Flow Chart](#). While these nominal times should be adhered to as closely as possible, the actual sampling times will be recorded and used for the determination of pharmacokinetic parameters.

If a subject misses an appointment, it will be rescheduled if possible. The relevance of measurements outside the permitted time windows will be assessed no later than at the Report Planning Meeting.

### **6.2 DETAILS OF TRIAL PROCEDURES AT SELECTED VISITS**

#### **6.2.1 Screening period**

After having been informed about the trial, all subjects will provide written informed consent in accordance with GCP and local legislation prior to enrolment in the study. For information

Proprietary confidential information © 2021 Boehringer Ingelheim International GmbH or one or more of its affiliated companies

regarding laboratory tests (including drug and virus screening), ECG, vital signs, and physical examination, refer to Sections [5.2.3](#) to [5.2.5](#).

### 6.2.2 Treatment period

Each subject will receive one dose of trial medication (BI 765080 or placebo) at Visit 2.

Trial medication will be administered as i.v. infusion by the investigating physician or [REDACTED] designee. Details on treatments and procedures of administration are described in Section [4.1.4](#).

Study participants will be admitted to the trial site on Day -1 and kept under close medical surveillance for at least 48 h following drug administration. The subjects will then be allowed to leave the trial site after formal assessment and confirmation of their fitness by the investigator or [REDACTED] designee. On all other study days, subjects will be treated in an ambulatory fashion.

For details on time points and procedures for collection of blood samples for PK analysis, refer to [Flow Chart](#) and Section [5.3.2](#).

The safety measurements performed during the treatment period are specified in Section [5.3](#) of this protocol and in the [Flow Chart](#). For details on times of all other trial procedures, refer to the [Flow Chart](#). AEs and concomitant therapy will be assessed continuously from screening until the end of trial examination.

### 6.2.3 Follow-up period and trial completion

For AE assessment, laboratory tests, recording of ECG and vital signs, and physical examination during the follow-up period, see Sections [5.2.2](#) to [5.2.5](#).

Subjects who discontinue treatment before the end of the planned treatment period should undergo the EoTrial Visit.

All abnormal values (including laboratory parameters) that are assessed as clinically relevant by the investigator will be monitored using the appropriate tests until a return to a medically acceptable level is achieved. (S)AEs persisting after a subject's EoTrial Visit must be followed until they have resolved, have been sufficiently characterised, or no further information can be obtained.

## 7. STATISTICAL METHODS AND DETERMINATION OF SAMPLE SIZE

### 7.1 STATISTICAL DESIGN – MODEL

The main objectives of this trial will be assessed by calculating descriptive statistics for safety as well as for PK [REDACTED] parameters, which will be compared between the treatment groups. Further analyses of these endpoints comprise the power model for assessment of dose proportionality.

### 7.2 NULL AND ALTERNATIVE HYPOTHESES

It is not planned to test any statistical hypotheses in this study.

Any confidence intervals computed are to be interpreted in the perspective of the exploratory character of the study; i.e., confidence intervals are considered as interval estimates for effects.

### 7.3 PLANNED ANALYSES

#### Analysis sets

Statistical analyses will be based on the following analysis sets:

- Treated set (TS): The treated set includes all subjects who were randomized and treated with at least one dose of study drug. The treatment assignment will be determined based on the first treatment the subjects received. The treated set will be used for safety analyses.
- Pharmacokinetic parameter analysis set (PKS): This set includes all subjects in the treated set (TS) who provide at least one PK endpoint that was not excluded due to a protocol violation relevant to the evaluation of PK or due to PK non-evaluability (as specified in the following subsection 'Pharmacokinetics'). Thus, a subject will be included in the PKS, even if he/she contributes only one PK parameter value for one period to the statistical assessment. Descriptive and model based analyses of PK parameters will be based on the PKS.

Descriptions of possible additional analysis sets will be provided in the TSAP, to be finalised prior to database lock.

Adherence to the protocol will be assessed by the trial team. Important protocol deviation (iPD) categories will be specified in the iPD specification file prior to trial initiation; iPDs will be identified no later than in the Report Planning Meeting and the iPD categories will be updated as needed.

Proprietary confidential information © 2021 Boehringer Ingelheim International GmbH or one or more of its affiliated companies

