## **CLINICAL TRIAL PROTOCOL SYNOPSIS**

Company name	Boehringer Ingelheim
Protocol date	22 October 2020
Revision date	10 May 2021
BI trial number	1450-0001
Title of trial	Safety, tolerability, pharmacokinetics, and pharmacodynamics of single rising intravenous doses of BI 765080 in healthy male subjects (single-blind, randomised, placebo-controlled, parallel-group design)
Principal Investigator	[REDACTED]
Trial site	[REDACTED]
Clinical phase	I
Trial rationale	In this first-in-human trial, the effects of single rising doses of BI 765080 on safety, tolerability, pharmacokinetics, and pharmacodynamics will be assessed as the basis for further development in patients with chronic kidney disease.
Trial objectives	To investigate safety, tolerability, pharmacokinetics, and pharmacodynamics following single rising intravenous doses of BI 765080
Trial endpoints	Primary endpoint to assess safety and tolerability of BI 765080 is the percentage of subjects with drug-related adverse events Secondary endpoints: 

– AUC0-∞ of BI 765080

– Cmax of BI 765080

Trial design	Single-blind, randomised within dose groups, placebo-controlled, parallel-group design
Number of subjects	
total entered	48*
each treatment	8 per dose group (6 on BI 765080 and 2 on placebo) * Additional subjects may be entered to allow testing of additional doses on the basis of experience gained during the trial conduct (e.g. preliminary PK data), provided the planned and approved highest dose will not be exceeded. Thus, the actual number of subjects entered may exceed 48, but is not to exceed 80.
Diagnosis	Not applicable

Proprietary confidential information © 2021 Boehringer Ingelheim International GmbH or one or more of its affiliated companies

Main criteria for inclusion	Healthy male subjects, age of 18 to 50 years (inclusive), body mass index (BMI) of 18.5 to 29.9 kg/m  (inclusive)
Test product	BI 765080 powder for solution for injection/infusion, 50 mg/vial
dose	Single doses of 1 mg, 10 mg, 25 mg, 50 mg, 100 mg, and 200 mg
mode of admin.	Intravenous as 30 min infusion
Comparator product	Matching placebo for BI 765080 concentrate for infusion solution
dose	Not applicable
mode of admin.	Intravenous as 30 min infusion

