### 3. DESCRIPTION OF DESIGN AND TRIAL POPULATION

### 3.1 OVERALL TRIAL DESIGN AND PLAN

This single-rising dose trial is designed as single-blind, randomised within dose groups, and placebo-controlled within parallel dose groups.

It is planned to include a total of 48 healthy male subjects in the trial. The subjects will be assigned to 6 groups consisting of 8 subjects per group; the groups will be dosed sequentially (see Table 3.1: 1). The investigator (after consultation with the sponsor) is allowed to alter the scheduled dose groups (e.g., add low and/or intermediate dose groups) based on experience gained during the study (for instance, based on preliminary PK data), provided the planned and approved highest dose is not exceeded. Thus, the actual number of subjects entered may be more than 48, but is not to exceed 80. Such changes may be implemented via non-substantial CTP amendments.

Within each dose group, 6 subjects will receive BI 765080 and 2 will receive placebo. Only one dose is tested within each dose group. For safety reasons, each dose group will consist of 3 cohorts. The trial medication will be administered in the following order:

- Cohort 1: 1 subject on active treatment followed by 1 subject on placebo (in total 2 subjects)
- Cohort 2: 2 subjects on active treatment (in total 2 subjects)
- Cohort 3: randomised to 3 subjects on active treatment and 1 subject on placebo (in total 4 subjects)

Between cohort 1 and cohort 2 there will be a time interval of at least 1 day, which is expected to be sufficient to detect relevant acute effects of BI 765080. Cohort 1 and cohort 3 will be separated by at least 2 days. This design ensures that between first and second active dose of each dose level, there is a time interval of at least 1 day, which covers the  $t_{max}$  of BI 765080 (end of infusion) and the period of highest risk / peak effect. If BI 765080 was safe and showed acceptable tolerability in the first two cohorts, the remaining third cohort of the respective dose level could be dosed as close as 10 minutes apart.

The dose groups to be evaluated are outlined in Table 3.1: 1 below.

Table 3.1: 1 Dose groups

Dose Group	1	2	3	4	5	6
Dose (mg)	1	10	25	50	100	200
Number of subjects	8	8	8	8	8	8
Subjects receiving placebo	2	2	2	2	2	2
Subjects receiving BI 765080	6	6	6	6	6	6

Proprietary confidential information © 2021 Boehringer Ingelheim International GmbH or one or more of its affiliated companies

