#### 4.1.3 Method of assigning subjects to treatment groups

Prior to the screening visit, subjects will be contacted in writing and informed about the planned visit dates. The subjects willing to participate will be recruited to dose groups (3 cohorts per dose group) according to their temporal availability. As soon as enough subjects are allocated to 1 of the 18 dose cohorts (3 cohorts per dose group), the following subjects will be allocated to one of the other dose cohorts. Therefore, the allocation of subjects to dose cohorts is not influenced by trial personnel, but only by the subjects' temporal availability. Because the study includes healthy subjects from a homogenous population, relevant imbalances between the dose groups are not expected.

Subjects will be assigned to treatments (active treatment or placebo) prior to the first administration of trial medication. For this purpose, the randomisation list will be provided to the trial site in advance. Numbers of the randomisation list will be allocated to subjects by drawing lots. Subjects are then assigned to treatment according to the randomisation list.

The randomisation procedure is described in Section [7.6](#).

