#### **7.3.1 Primary endpoint analyses**

The primary endpoint as specified in Section [2.1.2](#) will be derived according to BI standards. The analysis will be based on the treated set (TS) and will be descriptive in nature.

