## **7.6 RANDOMISATION**

Subjects will be randomised within cohort 3 of each dose group in a 3:1 ratio (active drug to placebo). Trial medication in cohorts 1 and 2 of each dose group will be administered in a fixed order (active - placebo - active - active; see Section [3.1](#)).

The sponsor will arrange for the randomisation as well as packaging and labelling of trial medication. The randomisation list will be generated using a validated system that uses a pseudo-random number generator and a supplied seed number so that the resulting allocation is both reproducible and non-predictable.

The randomisation list will contain additional blocks to allow for subject replacement (refer to Section [3.3.5](#)).

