6.3 SUBJECT SETS ANALYSED

The treated set (TS) and pharmacokinetic parameter analysis set (PKS) will be used as defined in the CTP, Section 7.3.

In addition, the following subject sets will be used:

All ECG analyses are performed on the TS, except for the exposure-response analyses, which are performed on the ECGPCS defined below.

- ECG PK concentration set (ECGPCS):
This subject set includes all subjects from the TS who provide at least one pair of a valid drug serum concentration and a corresponding (i.e. time-matched) ECG endpoint to be used in the exposure-response analyses. For placebo subjects, the

serum concentration is set to zero and hence always considered as valid. The decision whether a time deviation between PK blood sampling and ECG recording is acceptable (and thus whether the pair of values will be used) is to be made no later than at the RPM before data base lock. For subjects treated with active drug, the decision about concentration value validity needs to be made within the Clinical Pharmacology Group.

Table 6.3: 1 Subject sets analyzed

	Subject sets		
Class of endpoint	TS	PKS	ECGPCS
Primary endpoint	X		
Secondary PK endpoints		X	
Safety parameters (except for exposure-response analyses of ECG data)		X	
Exposure-response analyses of ECG data			X
Demographic/baseline characteristics	X		
Treatment exposure	X		

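### Does the Treated Set definition leave out the half of the subjects who are dosed in a fixed order?

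*Protocol*

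**What the plan says.** The Treated Set (TS) is defined in Protocol 7.3, under the heading Analysis sets: "The treated set includes all subjects who were randomized and treated with at least one dose of study drug". For the primary endpoint, Protocol 7.3.1 says: "The analysis will be based on the treated set (TS) and will be descriptive in nature". SAP 6.3 adds nothing to the definition: "The treated set (TS) and pharmacokinetic parameter analysis set (PKS) will be used as defined in the CTP, Section 7.3". The PKS and the ECGPCS are both drawn from the TS.

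On assignment, Protocol 7.6 says: "Subjects will be randomised within cohort 3 of each dose group in a 3:1 ratio (active drug to placebo", and then: "Trial medication in cohorts 1 and 2 of each dose group will be administered in a fixed order". The cohort list in Protocol 3.1 likewise attaches the word *randomised* to cohort 3 alone.

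Other passages use the word more broadly. The synopsis gives the design as "Single-blind, randomised within dose groups, placebo-controlled, parallel-group design", and the opening of Protocol 3.1 says the same in substance. Protocol 4.1.3, having just referred to all 18 dose cohorts, says: "Numbers of the randomisation list will be allocated to subjects by drawing lots".

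**The concern.** The TS definition has two conditions: randomised, and treated. If Protocol 7.6 decides who counts as randomised, subjects in cohorts 1 and 2 fail the first condition even though they were dosed. These include the sentinel subjects in cohort 1, the first to be dosed at each level, whom nobody would want to leave out of a first-in-human safety analysis.

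The TS is the denominator of the primary endpoint, so an exclusion there would carry through to the PK and ECG exposure-response sets. It would also weaken what the trial can say about safety. With no drug-related event among n subjects, the one-sided 95% upper bound on the event rate is 1 − 0.05^(1/n). That is 39.3% for n = 6 and 63.2% for n = 3. The plan does not compute this bound. It is shown only to indicate what halving an active dose group would mean.

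**Working it through.** **1. The planned total (Protocol 3.1 and 7.7).** Per dose group:

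| Cohort | Active | Placebo | Assignment in Protocol 7.6 |
|---|---|---|---|
| 1 | 1 | 1 | fixed order |
| 2 | 2 | 0 | fixed order |
| 3 | 3 | 1 | randomised 3:1 |
| Sum | 6 | 2 | |

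Six groups × (6 + 2) = 48, of whom 6 × 6 = 36 are active and 6 × 2 = 12 placebo. This reproduces the stated 48.

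**2. The literal reading (Protocol 7.3 combined with 7.6 alone).**
- TS = 6 × (3 + 1) = 24 of 48: 18 active and 6 placebo, with 3 of 6 active per dose.
- Left out: 48 − 24 = 24, also 18 active and 6 placebo.
- PKS at most 6 × 3 = 18 of 36, assuming placebo subjects provide no BI 765080 PK endpoint.
- ECGPCS, which includes placebo, at most 24 of 48.

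**3. The literal reading against the rest of the documents.**
- *Placebo group.* Protocol 3.2 and 7.3.4 and SAP 6.1 pool everyone given placebo, whatever the dose group. That is 12 subjects. The literal reading leaves 6, so it contradicts three explicit statements.
- *Active group size.* Protocol 7.7 justifies the sample size for exploratory safety and PK by 6 active and 2 placebo per group. The literal reading leaves 3 and 1.
- *Use of the word.* Protocol 7.3 (PK-relevant deviations) and 7.3.4 (deviations from assigned treatment) refer to randomised drug or treatment with no cohort limit.
- *Assignment procedure.* Protocol 4.1.3 covers 6 × 3 = 18 cohorts and assigns treatment from the randomisation list, with list numbers drawn by lot.

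**4. A reading that fits every passage.** Take *randomized* in the TS definition to mean holding a number on the randomisation list. The fixed order in Protocol 7.6 then describes the sequence in which active and placebo are given in cohorts 1 and 2, while the lot decides which subject takes which position. In cohort 1, for example, it decides who receives active and who receives placebo. All 48 subjects meet the definition, giving TS = 48, PKS at most 36 and ECGPCS at most 48.

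Two passages are deliberately not used here. The escalation requirement in Protocol 3.1 for evaluable subjects and the reporting rule for withdrawals in Protocol 3.3.4 both suggest wide inclusion, but neither defines membership of an analysis set.

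**The case for a change.** The best case for changing the text is that Protocol 7.6 is the section that governs randomisation, and 4.1.3 itself refers the reader to it. On that view the specific statement, cohort 3 only, should prevail over a general design label. In cohort 2 a lot cannot affect treatment, because both subjects receive active drug, so calling those subjects randomised is a stretch. Replacements take over the treatment of the subject they replace (Protocol 3.3.5), so they too are not randomised in the strict sense. Membership of the primary-endpoint set ought not to depend on interpretation, and a single sentence would settle it.

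Part of this stands. The wording of Protocol 7.3 and 7.6 does not match, and SAP 6.3 carries the mismatch forward. It is also true that the documents do not say outright whether lots are drawn in cohorts 1 and 2.

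What does not stand is the step from loose wording to a risk for the analysis. The narrow reading has to override the placebo-pooling rule in three places and the stated basis of the sample size. An analyst who built a TS of 24 would find only 6 of the 12 placebo subjects that SAP 6.1 requires in the pooled group, and the error would show in the first table. A new sentence would therefore lead to the same 48 subjects that the present text already gives when read as a whole.

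**Conclusion.** No change follows. The point is a clerical inconsistency in the word *randomized*. All treated subjects are plainly meant, and the documents contain enough to reach that reading without guesswork.

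The expected effect is 0 of 48 subjects lost. The 24-of-48 figure is a hypothetical bound that arises only if Protocol 7.6 is read in isolation from the synopsis and from 3.1, 3.2, 4.1.3, 7.3.4 and SAP 6.1. No alpha, power or sample-size figure is involved: Protocol 7.2 plans no hypothesis test and 7.7 rests on no power calculation.

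The counts assume six full groups of eight with no replacements and no added dose groups. Added groups with the same three-cohort layout would keep the same half-and-half split and lead to the same conclusion.
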